[figure not shown]
Official Title:	Mobile Health Obesity Wellness Intervention in Rural Older Adults (MOWI): Amulet Technology Development & Validation
NCT number:	NCT0304189
Document Type:	Study Protocol and Statistical Analysis Plan and Informed Consent Form
Date of the Document:	July 3, 2018

Overview: The study will: 1) Obtain input on feasibility, usability, and acceptability of using mHealth in behavior change by adapting a device for rural older adults; 2) Develop, refine and tailor MOWI in research settings; 3) Conduct MOWI in subjects' homes. The overall goal is to improve older adult physical function in rural areas and use the results as a basis for an R01 randomized trial testing the MOWI's delivery in the home.

Study Setting/Population: Dartmouth-Hitchcock (D-H) serves 1.5 million persons from a circumscribed area of rural New Hampshire/Vermont. The site of Lebanon, NH, is a typical rural New England town (16.2% aged ≥65 years; 95.4% Caucasian⁸³). Of 13,293 primary care patients ≥65 years old at D-H, 3,987 are study eligible (~30% obese⁸⁴). The Center for Health & Aging (CHA) has rooms for study assessments. In-home evaluations will use CHA video equipment.

Recruitment: As a Geriatrician working with an interdisciplinary team, I have ready access to potential subjects from a practice panel of ~3000 older adults. In addition the Centers for Health and Aging provide a venue for recruitment, as indicated by successfully recruiting 111 elderly subjects this past year for pilot studies by 3 junior faculty. Patients meeting study criteria will be identified using record review and e-mailed/mailed letters describing the study (after HIPAA waiver). Posters/handouts will be placed strategically at D-H. Colleagues will give information materials to patients requesting permission for contact by the study research assistant. With respect to the qualitative component, the PI will recruit 6 clinicians (from 87 in the provider network) to participate in interviews. [name] will use the CHA's extensive aging services network to recruit 4 leaders of aging services organizations for study participation.

FIGURE 2: STUDY OVERVIEW

Selection Criteria: Focus groups, interviews, and usability testing will target English-speaking obese older adults (age ≥65 years and BMI ≥30kg/m²¹⁷ or waist circumference ≥88/102cm⁸⁵ in females/males). Excluded from eligibility are adults with severe mental or life-threatening illness, dementia, substance use, history of bariatric surgery, suicidal ideation, unable to provide consent/perform measures, or residing in a nursing home. Aim 1a provider interviews will target English-speaking, licensed, outpatient, primary care clinicians and community aging service program directors. Older adult participants in Aims 2 & 3 will require the presence of home Wi-Fi high-speed internet, medical clearance, have less than a 5% weight loss in the past 6 months, and be without advanced co-morbidity, exercise restrictions⁸⁸ or involvement in other research studies.

Screening/Consent: Subjects expressing interest will be mailed/mailed forms, evaluated by chart review to confirm eligibility, and those meeting criteria invited to an RA-led session to verify final eligibility, review and complete consent forms, and answer queries. Competence for consent will be assured by: no diagnosis of dementia (all Aims) and a Callahan score ≥4 (Aims 2 & 3). Written consent will be obtained before enrollment. The RA will obtain screening/baseline measures, and provide a list of contact details (see Human Subjects).

Aim 1b (Adapt Amulet): Adapt a novel mHealth device (Amulet) to assess geriatric functional measures in a sample of older, obese adults: Amulet will be modified to measure functional outcomes (activity type, strength, gait speed) in older adults supporting MOWI's exercise component using self-monitoring and feedback. This device (Figure 3) provides an adaptable platform for remote sensing and health behavior change. I chose Amulet due to its potential for team science and as an ecologic momentary assessment system⁹⁶. It measures more about human activity unlike devices^{82,97} that measure steps, expenditure, or sleep^{81,98,99}. Custom body-area health network applications measure, monitor and provide continuous, secure user feedback¹⁰⁰. The prototype wrist-worn device does not rely on other devices (ie: smartphone) to function. Battery life will likely exceed 7 days. The Amulet display provides personalized programmable reminders (blinking lights, textual display, or vibration) and audio-visual feedback to allow goal attainment. A 9-axis gyroscope, accelerometer, and magnetometer integrates sensors capturing motion, speed, isometric exercise data and activity type (sedentary, walking, running). Low-energy Bluetooth 4.0 can connect with other nearby devices. A mini-USB port and micro-SD card will allow for a 2-way data transfer.

[name] team will develop and configure applications assessing: steps/distance; strength; activity type; activity feedback. Objective measures will be validated with Amulet. Amulet will sample data and detect stepping motion using algorithms ascertaining activity type^{101,102} and step counts¹⁰³. Distance is calculated as steps × distance/step. Upper limb strength will be assessed using sensors placed on a Thera-

band¹⁰⁴ handle connected to a strain gauge placed in series reading the combined force experienced using an analog-to-digital converter¹⁰⁵, communicating back to Amulet.

Usability evaluations during technology deployment will ensure a user-centered design, using videotaped sessions to enable careful review by the development team. Open-ended semi-structured interviews to the first 5 subjects will consist of subject-initiated tasks involved in Amulet's operation. Continuous commentary (Think Aloud usability method^{109,110}; see Appendix) with non-verbal/verbal reactions will be used to evaluate Amulet's ease of use, complexity, and design flaws. Subjects will rate their confidence in using the system (see Appendix). A semi-structured approach will be employed including questions such as: What are helpful formats for feedback messages?; What types of Amulet data will be most useful?; How can mHealth be of maximum utility to users?; What are the highest priorities for feedback? Adaptive testing will be performed as it is difficult to fully develop messages prior to pilot testing.

Aim 1 informing future work: Focus groups, interviews and usability testing will be used to create the intervention manual, adapt the Amulet, and optimize Aim 2 (and to the Amulet/Telehealth teams, allowing refinement prior to integration into future cohorts and tailoring content to meet older adult needs. Formative mixed methods will be used to identify and address design and content flaws and unanticipated challenges as part of a critical feedback loops using staged, iterative, usability testing.

Recruitment and Retention Strategies

Participants will be recruited from referrals from Family Medicine/General Internal Medicine providers (Primary Care), providers from the Dartmouth Weight & Wellness Center, and community members attending the Dartmouth Center for Health and Aging (DCHA). I will inform clinicians of Family Medicine and General Internal Medicine and the staff at the Weight & Wellness Center of the proposed study during section meetings. [name] has an extensive network of community-care providers and will send e-mails/letters to the CHA's listserv and mailing list requesting participation. Posters will be placed in each examination room, in the patient waiting areas and in common areas of the DCHA. All posters will have been pre-approved by DHMC patient/family advisors and the Committee for the Protection for Human Subjects. Additionally, postings in the DCHA quarterly newsletter, the DHMC weekly D-H Today online bulletin, the weekly Geisel School of Medicine at Dartmouth newsletter, and electronic mailing lists will promote the study. We anticipate advertising in the local newspaper as well. A dedicated phone number and e-mail will be assigned to this study.

Patients will be identified from the PI's clinical practice group at D-H, word of mouth, or other means as indicated below. We will also identify prospective individuals fulfilling basic eligibility criteria after obtaining a HIPAA waiver for electronic record review from the Committee for the Protection of Human Subjects. A pre-assessment eligibility would be performed to limit the burden on patients should they be ineligible after full informed consent for the requisite aims. This will allow the investigators to query our electronic medical record and if necessary send targeted messages and/or letters to individuals that may possibly qualify for this study. If needed, the study staff will send a letter to prospective individuals requesting their involvement either by mail or email (through the electronic medical record). This letter will describe the study and provide contact information for those interested. The CTO will also have details of the study. Any individuals that have expressed interest will be contacted by the team by phone or by email which will be the most preferable method of communication. A pre-screening questionnaire or electronic link to RedCAP (See below) or by phone will be mailed/mailed to participants (depending on patient preference).

As part of Aim 1a, eligible patients will be asked to participate in qualitative focus groups and individual semi-structured interviews with a member of the team. It is anticipated that the focus group will occur 4-6 weeks after interest is expressed. The investigators will perform four separate patient focus groups. Semi-structured interviews will take place for clinicians and community leaders of health and senior centers. At the time of communication, the consent form will be sent to these individuals for review (paper or electronic) and if they agree to the terms of the consent, the individuals will attend these sessions at a mutually convenient time for the study participants and the Research Team. A reminder letter will be sent either via myDH (through the electronic medical record) by the PI, and/or a hard copy letter to the patient's address.

As part of Aim 1b, eligible patients will be asked to attend the DCHA to confirm eligibility and informed consent process by the RA/PI (See Section on *Informed Consent Procedures* for Full details). Those ineligible will be informed by the team and any information will be destroyed. We anticipate that eligibility to study onset will be roughly 4-6 weeks after screening.

As part of Aim 2 and 3 (including the pre-pilot Aim 2), eligible patients will be asked either to attend a baseline visit with the RA or PI at the DCHA to confirm study full eligibility for measurements and full informed consent process by the RA/PI (See Section on *Informed Consent Procedures* for Full Details). Those ineligible will be informed by the team and any information will be destroyed. We anticipate that eligibility to study onset will be roughly 4-6 weeks after screening. The patient's primary care provider will provide medical clearance prior to study enrollment and sign a paper or electronic form allowing the individual to undergo this intervention. They will be kept informed of any abnormal symptoms or problems throughout the study.

The investigators recognize that this intervention may lead to attrition. To reduce the risk of participant drop-out, participants will be reminded of sessions with a phone call, e-mail, and Amulet messaging reminder from the RA. Individuals will be compensated with sandwiches/snacks plus \$25 gift card for the focus groups of the qualitative aim (Aim 1a), \$25 gift card for the subject semi-structured interviews, a nominal \$10/hour payment for the prevalidation phase of Aim 1b (cash, gift-card), a \$25 gas card each for Aim 1b, \$100 for completing >80% of the visits and assessments for the three-month program (Aim 2) - \$25 per assessment, and \$200 for completing >80% of the visits and assessments at 6-months (Aim 3). Payment will be made at study conclusion according to institutional policies. They will also receive a fixed schedule of items (pens, notepads, thank you cards) to recognize their participation to date. Participants will have the option of declining such incentives at any time. We will provide a \$25 gas card or equivalent for each visit (Aim 4).

No involvement of special vulnerable population such as fetuses, neonates, pregnant woman, children, prisoners, institutionalized individuals or others who may be considered vulnerable will be included in this study. The study will be a single-arm study and there will be no assignment to a study group for this study.

Retention

We recognize that attrition rates in obesity studies range between 25-50%. For Aim 1a (qualitative studies), we will target 4 focus groups of 6-8 individuals (24-32 individuals total), 6-8 individual semi-structured interviews, 6 primary care clinicians, and 4 community leaders for a maximum total of 50 individuals. For Aim 1b, we anticipate recruiting 75 individuals for a target of 60 individuals. Conservative estimates suggest that 14 individuals need to be recruited to allow for 16 individuals for Aim 2 at study conclusion. For Aim 3, our target is 40 individuals. We anticipate recruiting 53 individuals. We believe that these targets are feasible with our local population. We anticipate recruiting individuals in one wave for Aim 1, two waves for Aim 2, and in 4 waves for Aim 3 to reach target enrollment and completion. Should we exceed target enrollment and completion, we will continue gathering measurements on all individuals. With the new arm (MOWI-P), we anticipate recruiting an additional 16 subjects. For Aim 4 (Weight Maintenance), we anticipate recruiting 60% of each of the original sample for Aim 2 (ie: 4 waves @ 8 = $32 \times 0.6 =$ approximately 19 subjects).

STATISTICAL DESIGN AND POWER

Aim 1 (Qualitative assessment) will use mixed-methods to adapt Amulet and MOWI for use in rural older obese adults.

Aim 1b (Adapt Amulet): Adapt Amulet to assess functional measures: Agreement/reliability for upper/lower strength (Thera-bands and STS), gait speed, and steps will be calculated. Descriptive statistics will outline distributions, mean differences/ ratios assessing Amulet's measures to corresponding steps, speed or strength, and for usability testing. Relative/absolute test-retest reliability of mean differences between test/retest using 95% confidence intervals and standard error of mean to examine bias and intra-class coefficients will be reported. Paired t-test will test for bias. Scatterplots and Bland-Altman plots for miscalibration will be viewed, and a relation of variance to mean (data heteroscedasticity) to assess agreement between measures.

Data and Safety Monitoring Plan

Per the instructions for the “Human Subjects” section of PHS-398/SF424 (R+R) the proposed study intervention could have harmful effects but does NOT meet the criteria for an NIH-defined Phase III trial.

To ensure participant safety, data integrity and validity, the Research Assistant will meet with the Principal Investigator monthly, and will be responsible for reviewing the following: number of subjects completing the protocol; subject withdrawal and sources of data loss; any serious or minor adverse consequences and actions taken to remedy the issue; new, timely information that could impact efficacy and/or safety of the program or procedures. The meeting reports will be forwarded to the Committee for the Protection of Human Subjects at the time of annual review and serious events will be reported per institutional regulations.

The current intervention is not an experimental agent and its proposed risk to individuals is likely considered low. We anticipate that there will be a low risk of adverse medical events associated with this intervention. A physician will be available on the premises during all intervention sessions and monitor patient progress and/or adverse events during each session and be responsible for monitoring the data and safety for this proposal. However, we intend on establishing an independent data safety monitoring process that will include an independent data safety monitoring board (DSMB). The committee will consist of experienced researchers in the Department of Medicine and The Dartmouth Institute at the Geisel School of Medicine at Dartmouth. Such members will consist of researchers who are not involved in the development or execution of this proposal. Per institutional policies, no investigators will have any conflict of interests with or financial stakes in the research outcome. This independent board will follow the policy for data and safety monitoring published by NIH and be responsible for reviewing the following information: adverse consequences (whether serious or minor) to any subject and actions taken to remedy the problem; data quality, completeness, timeliness; performance of the study site; reviewing the entire IRB-approved study protocol, manual of procedures with regard to safety, recruitment, intervention, data management, quality control, analysis and informed consent documents with regard to applicability and readability; recruitment and retention; adherence to protocol; maintenance of confidentiality; external factors impacting safety or ethics of the study; and new or evolving information regarding the expected efficacy and/or safety of the MOWI intervention. Additionally, the DSMB will review the study in relation to intervention effects, gender and minority exclusion; propose appropriate analyses and periodically review developing data on safety and endpoints; consider the rationale semi-annually for continuing the study; review and make recommendations on proposed protocol changes during the trial. All recommended changes to the protocol will be adhered to by the PI. The board will identify relevant data parameters and the format of how the information will be regularly reported. Written reports of each meeting will be sent to the program officer and additional reports as needed, in addition to providing timely advice on issues regarding data discrepancies. They will review manuscripts of trial results. In addition, they will recommend subject recruitment be initiated after receipt of a satisfactory protocol and/or postpone recommendations for initiation of subject recruitment until after the receipt of satisfactory revised protocols. Summary reports of the meetings will be sent to the CPHS at the time of annual reviews. The monitoring committee will ensure safe and effective conduct of the intervention and recommend conclusion of the intervention when significant benefits or risks have developed or the intervention is unlikely to be concluded successfully. All monitoring will be timely and effective. Data from the Research Assistant and Biostatistician will be forwarded to the DSMB for review (and to the Program Officer upon request). The DSMB will conduct reviews of the study every 6 months.

All information will be kept confidential during all phases of the intervention, including monitoring, preparation of interim results, review and response to monitoring recommendations. Monitoring will also consider external study factors when interpreting data, including scientific or therapeutic developments that can impact participants. The results of the trial will be forwarded upon publication of its results to all subjects at the conclusion of the intervention. The team will also provide the subject’s healthcare providers with appropriate information, as needed, concerning the individual.

Adverse Event Reporting

Serious, unexpected adverse events (SAE) related to study participation are anticipated to be rare. Study personnel will be trained to report all adverse events. In addition, screening for adverse events potentially related to the study intervention will occur during the routine administration of study assessment measures. These interview-based indicators will augment required SAE reports by study personnel, including specific items in the assessment interviews evaluating episodes of muscle or fall-related injuries, unexpected medical events, medical emergency room admissions, medical hospitalizations, or unplanned medical clinic

visits. If an SAE occurs, the PI will report the event to the Dartmouth CPHS using the CPHS Adverse Event Form, to the DSMB, and to the NIA Program Officer within 10 days of the study's knowledge of the SAE (if unanticipated) unless otherwise requested by the DSMB. The PI, in consultation with co-investigators and others, as needed, will review the adverse event report and gather other information as needed to investigate the event and determine the need for subsequent action. Any subsequent action will be documented and reported to the CPHS. In addition, any SAE will also be reported to the NIH program officer and they will be informed of any actions taken by the CPHS as a result of its continuing review. The CPHS will review each reported adverse event to determine whether: the participants in the study should receive additional information related to continuing their participation; the protocol, study plan or consent form should be modified; or the study should be temporarily suspended. If the CPHS determines that some action in response to the adverse event is necessary, the CPHS will promptly inform the PI. All deaths will be reported in an expedited manner, normally within 24 hours of the study's knowledge. The report of death will also be submitted to the NIA Program Administrator and to the CPHS and to the DSMB Chair.

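### Aim 2 recruitment figures are impossible as printed: 14 recruits cannot give 16 participants at conclusion, and the intended pair cannot be recovered from the text

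*Combined protocol and SAP*

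**What the plan says.** All the counts are in one paragraph of the combined protocol and SAP, under Retention. It opens by citing attrition of 25-50% in obesity studies, without a follow-up time, and then sizes each aim:

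- Aim 1b: "For Aim 1b, we anticipate recruiting 75 individuals for a target of 60 individuals".
- Aim 2: "Conservative estimates suggest that 14 individuals need to be recruited to allow for 16 individuals for Aim 2 at study conclusion".
- Aim 3: "For Aim 3, our target is 40 individuals. We anticipate recruiting 53 individuals".
- Waves: "two waves for Aim 2, and in 4 waves for Aim 3 to reach target enrollment and completion".
- MOWI-P: "With the new arm (MOWI-P), we anticipate recruiting an additional 16 subjects".
- Aim 4: "we anticipate recruiting 60% of each of the original sample for Aim 2 (ie: 4 waves @ 8", which the text multiplies out to 32 and then to approximately 19.

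The payment terms under Recruitment and Retention Strategies give the durations: "completing >80% of the visits and assessments for the three-month program (Aim 2") for one aim and "completing >80% of the visits and assessments at 6-months (Aim 3") for the other. No attrition rate is stated for Aim 2, and no other section of the supplied text gives a different Aim 2 recruitment number.

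**The concern.** A recruitment figure allows for dropout, so it must be at least as large as the number wanted at the end. For Aim 2 it is smaller. The sentence presents itself as conservative and follows directly after a citation of substantial attrition, so it contradicts its own purpose.

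At stake is whether Aim 2 has a usable enrolment or completion target. Under the Data and Safety Monitoring Plan, the research assistant and principal investigator review completion counts monthly. The DSMB reviews recruitment and retention, and may recommend ending the intervention if it is unlikely to finish successfully. For Aim 2, neither has a benchmark to measure against.

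A smaller question concerns Aim 4. Its base of 32 in four waves is described as the Aim 2 sample, yet the same paragraph gives Aim 2 two waves and the numbers 14 and 16.

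**Working it through.** **Inputs**, all from the Retention paragraph: Aim 2, 14 recruited and 16 at conclusion; Aim 1b, 75 and 60; Aim 3, 53 and 40; cited attrition 25-50%; Aim 2 in two waves; MOWI-P 16; Aim 4 fraction 0.6. The three-month and six-month durations come from the payment terms.

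**1. The neighbouring aims.** With recruits = completers / (1 - attrition):
- Aim 1b: 60 / (1 - 0.20) = 75, as stated. Implied loss 1 - 60/75 = 20.0%.
- Aim 3: 40 / (1 - 0.25) = 53.3, stated as 53. Implied loss 1 - 40/53 = 24.5%.

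The usual formula therefore reproduces both.

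**2. Aim 2 as printed.** Retention = 16/14 = 114.3%; attrition = 1 - 16/14 = -14.3%. No attrition of zero or more gives 14. Even with no loss at all, 16 recruits are needed.

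**3. What the sentence might have meant.**
- *Numbers swapped (16 recruited, 14 finishing):* loss = 1 - 14/16 = 12.5%, half the lower end of the cited range. At 25-50%, 16 recruits would leave 16 x 0.75 = 12 down to 16 x 0.50 = 8.
- *16 completers is the real target:* 16/0.75 = 21.3, rounded up to 22; 16/0.50 = 32. So about 22 to 32 recruits.
- *14 is the real enrolment:* 14 x 0.75 = 10.5; 14 x 0.50 = 7. So about 7 to 10.5 finishing.

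**4. Allowing for Aim 2's shorter duration.** Assume a constant dropout rate, which the documents do not state. Aim 3's six-month retention of 40/53 then becomes sqrt(40/53) = 0.869 over three months, a loss of 13.1%. Applied to 16 recruits, 16 x 0.869 = 13.9 finish.

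**5. Aim 4.** 4 x 8 = 32 and 32 x 0.6 = 19.2, so the stated product is right. Two Aim 2 waves of 8 make 16, and adding the 16 for MOWI-P gives 32. Aim 3 is the only aim given four waves, and it does not fit: 40/4 = 10 and 53/4 = 13.25 per wave, not 8.

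**The case against.** The strongest reply is that this is a plain slip: the two numbers were transposed, and everyone will read the sentence as 16 recruited and 14 finishing. There is real support for that. Scaling Aim 3's loss to three months gives 13.9 of 16, very close to 14. Two waves of 8 make 16, which matches the wave size in the Aim 4 sentence, whereas 14 in two waves is 7. The cited 25-50% carries no duration, so it does not rule out 12.5% over three months.

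This makes transposition plausible but does not establish it. The sentence attaches 16 to the number at conclusion. A 12.5% loss lies below the only range the paragraph cites, under a claim to be conservative. The agreement with Aim 3 depends on an assumed constant dropout rate. Only the sponsor can say which figure was planned, so the write-in of 16 and 14 should not be made on a reader's behalf.

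On Aim 4, the reply largely succeeds. The arithmetic is correct, the MOWI-P subjects are named in the sentence immediately before, and the wording about each part of the sample may point to more than one cohort. A reader might infer that the Aim 4 target is wrong and should be 60% of 16, about 10, or of 14, about 8. The documents do not support that, since about 19 is the stated target and a sensible route to 32 exists. What remains is an ambiguity: the base is called the original Aim 2 sample, MOWI-P is called a new arm, and Aim 2 is given two waves.

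It is also fair to say that the supplied text has no design section for Aim 2, Aim 3, MOWI-P or Aim 4, and the overview figure is not shown. Some of what looks unexplained may be explained there.

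**Conclusion.** The Aim 2 sentence is impossible on its face and should be corrected; this needs no assumption beyond completers not exceeding recruits. The implied attrition is -14.3%, against 20.0% and 24.5% for the two aims sized beside it.

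The correct pair is not determined by the text. The candidate readings run from 14 recruits with about 7 to 10.5 finishing, through 16 with 14 finishing, to about 22 to 32 recruits for 16 finishing. The first and last rest on the cited 25-50% applying to Aim 2.

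A reader might also infer that Aim 2 is underpowered. The documents do not support that: no Aim 2 power statement or test in the supplied text depends on these figures. The effect is on recruitment and completion targets in a single-arm study. The Aim 4 base is a request for clarification, not an error.

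**What to change.** Replace the Aim 2 sentence with one consistent set: the number planned for recruitment, the assumed attrition rate, and the completers that follow from the two. Add a clause justifying the rate against the cited 25-50%; if a lower rate is assumed because Aim 2 lasts three months, say so. Where planned enrolment stays fixed, lower the stated number of completers to what that enrolment delivers rather than add patients.

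As a minor clarification in the same paragraph, state that the Aim 4 base of 32 is Aim 2 plus MOWI-P (16 + 16), if that is what is meant, and whether each 16 counts recruits or completers. At present 16 is a number at conclusion for Aim 2 and a number recruited for MOWI-P.

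The cost is two reworded sentences, with no added visits or data. There are no added patients if enrolment is kept and the completer figure is lowered. If the sponsor instead confirms 16 completers as a firm target, enrolment has to exceed the printed 14: at least 16 with no loss, and about 22 to 32 over the cited range.

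### Does the Aim 1b paired t-test need a named comparison, a confidence interval and an acceptable-error limit added to the plan?

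*Combined protocol and SAP*

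**What the plan says.** The Aim 1b paragraph under Statistical Design and Power sets out several analyses.

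- Accuracy against the reference is described first: "Descriptive statistics will outline distributions, mean differences/ ratios assessing Amulet's measures to corresponding steps, speed or strength".
- Test-retest reliability follows, with mean differences examined "using 95% confidence intervals and standard error of mean to examine bias and intra-class coefficients will be reported".
- Then comes the single hypothesis test: "Paired t-test will test for bias". Neither the pair nor the null value is given.
- Agreement is then examined graphically: "Scatterplots and Bland-Altman plots for miscalibration will be viewed", together with a check on whether the spread of the differences changes with their level.

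The sample size is in the Retention section: "For Aim 1b, we anticipate recruiting 75 individuals for a target of 60 individuals". No power, precision or margin is given for it.

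On purpose, the Aim 1b methods section says "Objective measures will be validated with Amulet". The same section describes the device as a prototype ("The prototype wrist-worn device does not rely on other devices"), and the section on how Aim 1 informs later work says "Formative mixed methods will be used to identify and address design and content flaws".

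**The concern.** Validation is a stated purpose: it is in the trial's title, and the Overview says the results will support a later randomised trial. Whether a device is accurate enough depends on the size of its error read against a tolerance. A paired t-test asks only whether the mean error can be distinguished from zero, and the answer depends on scatter. A noisy device can pass unflagged, while a precise one with a trivial offset is declared biased.

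Three gaps add to this.

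- The pair is unnamed, and the preceding sentence uses the word bias about test-retest, so two analysts could test different quantities.
- Repeatability gets a planned interval, but accuracy against the reference gets only descriptive summaries.
- The Bland-Altman plots are to be looked at, with no promise to report limits of agreement and no tolerance to read them against.

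If agreement were judged by this test, a statement that a measure had been validated would have no fixed meaning.

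**Working it through.** **Inputs.** From the documents: n = 60 (target) and n = 75 (recruited). Assumed: null of zero, two-sided 5% level, one pair per person, normal differences, and every bias, SD and tolerance below (in % of the reference value).

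**The plan's own figure.** The target of 60 cannot be derived, because no SD, effect, margin or power is stated. The step to 75 matches 60/(1 − 0.20) = 75, a 20% loss that the text does not state. This has no bearing on the point here.

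**What the t-test can detect.** It is significant when |mean difference| > t(0.975, n−1)/√n × SD.

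- n = 60: 2.001/7.746 = 0.258 SD
- n = 75: 1.993/8.660 = 0.230 SD

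The chance of a non-significant result comes from the noncentral t with noncentrality (bias/SD) × √n. At n = 60:

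| Bias | SD | Bias/SD | Non-significant |
|---|---|---|---|
| 5% | 10% | 0.50 | 3% |
| 5% | 20% | 0.25 | 52% |
| 5% | 30% | 0.167 | 75% |
| 1% | 2% | 0.50 | 3% |

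In the last row the limits of agreement are 1 ± 1.96 × 2, about −3% to +5%, yet the test is significant in 97% of studies. So the general criticism of the test as a measure of agreement is correct.

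**Does the plan rely on it?** There are two readings of the sentence.

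1. Test versus retest. The 95% interval for that difference is already planned.
2. Amulet versus reference. The test needs the mean difference and its standard error, and these give the 95% interval directly: mean ± 0.258 SD at n = 60.

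On either reading, the Amulet-reference differences are summarised and plotted. A Bland-Altman plot is built from their mean and SD, which also give the limits of agreement, mean ± 1.96 SD. The 95% interval of each limit has half-width t × √(1/n + 1.96²/(2(n−1))) × SD:

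- n = 60: 2.001 × √(0.01667 + 0.03256) = 0.444 SD
- n = 75: 1.993 × √(0.01333 + 0.02596) = 0.395 SD

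Nothing has to be collected or modelled beyond what is planned.

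**Would a formal acceptance rule help?** Take a bias of 5%, a tolerance of ±30% for the limits of agreement, and n = 60 (2,000,000 simulated studies per row). A measure passes either when both estimated limits lie inside the tolerance, or when the outer 95% bounds of both do. Under the second rule it fails if the interval of either limit lies wholly beyond the tolerance, and is otherwise undecided.

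| SD | True limits | Pass, estimates | Pass, outer bounds | Undecided (outer-bound rule) |
|---|---|---|---|---|
| 10% | −14.6 to 24.6 | 99% | 66% | 34% |
| 12% | −18.5 to 28.5 | 73% | 11% | 89% |
| 15% | −24.4 to 34.4 | 10% | 0.2% | 79% |
| 20% | −34.2 to 44.2 | under 0.1% | under 0.1% | 8% |

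At SD 12% the true limits lie inside the tolerance, yet the stricter rule leaves 89% of studies undecided. When the upper limit sits exactly at 30%, with SD (30 − 5)/1.96 = 12.76%, the looser rule passes 52% and the stricter 4%. The choice of rule is a trade-off that the documents' figures do not settle, and the tolerance would have to come from the sponsor.

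**The case for a change.** The strongest case for a change is that this is a validation aim and yet accuracy, the quantity that matters most, is the one without a committed interval. An unnamed test leaves a choice open until after the data are seen. A tolerance fixed beforehand costs only wording and prevents a measure being called validated on whatever error happened to be found. The simulations add that the choice of acceptance rule can alter the conclusion, which argues for making it early.

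Much of this stands as description: the pair is unnamed, the interval is written for test-retest only, and no tolerance appears in the published text. Naming the pair and printing the interval and the limits of agreement would be good reporting.

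It does not amount to a fault in the plan. The plan never says that a non-significant test means agreement, and no go/no-go decision depends on Aim 1b. The absence of a tolerance is also less certain than it looks. The analysis paragraph covers STS and gait speed, but the published methods text does not describe the reference procedure for either, and its citations jump from 105 to 109. That suggests, without proving, that some Aim 1b method text is not in the public document.

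**Conclusion.** No change follows. The test cannot show agreement, but the plan does not ask it to, and the analyses that describe device error are already there. Followed as written, the paragraph gives a sound formative account of bias, scatter and repeatability. What is left open is detail that a competent analyst would supply from the same data: which pair was tested, an interval of ± 0.26 SD on the mean difference and ± 0.44 SD on each limit of agreement at n = 60 (± 0.23 and ± 0.39 SD at n = 75). No efficacy result is affected; at most the validation statement for a measure would be less crisp.

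A tolerance fixed in advance is desirable but optional at this stage, and the sample was not sized for a pass/fail verdict. The conclusion rests on the formative role of Aim 1b and on the absence of any decision tied to the test. The probabilities rest on assumed biases, SDs and tolerances, with one pair per person. Had the plan declared measures valid on a non-significant t-test, the conclusion would be different.
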